9.5 Study size

Below we describe key target group sizes, vaccination coverage and recorded influenza infection incidences in the three Nordic countries for the 2023-2024 season. This provides a good indication of the possible study size for the 2024-2025 season. We expect to include at least 3.2 million individuals who are included in the key target groups for seasonal influenza vaccination across the 3 Nordic countries.

In Denmark, the total population of individuals aged 65 years and older, along with the population at increased risk below 65 years of age, consisted of 1,211 million and 554,780 individuals, respectively, as of 20 December 2024. (39) From 1 October 2024 to 20 December 2024, influenza vaccination coverage in these target groups was 75.6% and 29.2%, respectively. (39) As of 13 January 2025, there were 700 confirmed cases of influenza, including 414 hospitalisations, in older adults above 65 years. (40)

In Finland, the total population of individuals aged 65 years and older was 1,315 million with a vaccine coverage of 61% during the 2023-2024 season. The population at increased risk aged between 18 and 64 years comprised of 0,52 million individuals. The influenza A incidence was 65.5 per 10,000 person-years, and influenza A hospitalisation incidence was 5.4 per 100,000 person-years. As of 20 January 2025, there were 3224 confirmed cases of influenza in the Finnish population, including 81 hospitalisations due to influenza in adults aged 65 years and above. (41,42)

In Sweden, the total population of elderly 65 years and above in the four regions under study comprise of 280,000 individuals, with national influenza vaccination coverage of 69% in the 2023/2024 season. (43)

We will utilize all available data to us from the countries' nationwide registers (Denmark and Finland), and regional data sources (Sweden). The statistical power of our proposed study will be reflected in the 95% CI of the effectiveness estimates. We expect to have robust statistical precision for the most widely used influenza vaccine brands within the current season. (44,45)

9.6 Data management

No individual-level data can or will be shared between countries or with EMA. Each country is the sole data owner and controller of their own data. Only country-specific results will be shared and combined results will be generated using meta-analysis. Data management and statistical analyses will be conducted using a Common Data Model (CDM), by which national register data are standardised to a common structure, format and terminology in order to allow the same statistical programming scripts to be used in each country. The CDM standardizes the structure of input variables and datasets, ensuring consistency across the three Nordic countries. It is specifically designed to facilitate vaccine effectiveness analyses within the Nordic healthcare setting. The use of a CDM with common statistical programming scripts will facilitate efficient use of resources and reproducibility of the statistical analyses.

The analytical group in Denmark will code the statistical analyses using R-scripts (R version 4.2.2.). The R-scripts will be made available on GitHub (also during the programming phase to facilitate input and comments). The analysts in each of the participating countries will then run the R-scripts and return the output to Denmark. The country-specific results will be combined using meta-analysis in Denmark.

9.7 Data analysis

Procedures

We will use a matched cohort design to evaluate the effectiveness of seasonal influenza vaccine in comparison with not receiving a seasonal influenza vaccine. Individuals who have received the vaccine will be matched on the day of vaccination with individuals who have not yet received the vaccine. Individuals will be matched on age (5-year bins), sex, region of residence, and selected comorbidities. The day the seasonal vaccine dose was administered within each matched pair will serve as the index date for both individuals. If individuals who were included as a matched non-vaccinated individual

(i.e., a reference individual) receive a vaccine later than the assigned index date, the pair will be right-censored on the day the non-vaccinated individual is vaccinated. In these cases, the non-vaccinated individuals will be allowed to potentially re-enter as vaccine recipients in a new matched pair on that given date.

Statistical analysis

We will follow individuals from day 14 after the index date (to ensure full immunisation) up until the day of an outcome event, death, emigration, or end of the study, whichever occurs first. Additionally, we will censor individuals with a positive PCR test for influenza in our follow-up period 14 and 30 days after the test (as a positive test will be part of the outcome definitions) for the influenza hospitalisation and death outcome analyses, respectively. We will right-censor matched pairs when the reference unvaccinated individual receives a vaccine during follow-up. Cumulative incidences will be estimated by the Aalen-Johansen estimator, and from these we will calculate the comparative VE as $1 - \text{risk ratio}$ at the start of week 18 (depending on data availability) since index date. The corresponding 95% CI will be calculated using the delta method. Country-specific estimates will be combined by random-effects meta-analyses implemented using the *mixmeta* package in R.

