7. RATIONALE AND BACKGROUND

Seasonal influenza remains a major public health concern, with a disproportionate impact on older adults aged 65 years and above and individuals who are at increased risk of severe complications, hospitalizations, and mortality associated with influenza infections. Vaccination continues to be the cornerstone of influenza prevention strategies. However, approaches to generate robust estimates of the effectiveness of influenza vaccines has been a subject of extensive research and debate (1).

Several studies have demonstrated moderate effectiveness of seasonal influenza vaccination in elderly populations. Meta-analyses have shown that influenza vaccination is moderately effective against laboratory-confirmed influenza in elderly people during epidemic seasons (2,3). A comprehensive individual participant data meta-analysis by Darvishian et al. examined the effectiveness of seasonal influenza vaccination in community-dwelling elderly people (3). The analysis included 4975 individuals (1829 cases and 3146 controls) from test-negative case-control studies. The researchers observed that influenza vaccination was moderately effective against laboratory-confirmed influenza in elderly people during epidemic seasons when the vaccine matched the circulating type, with a pooled vaccine effectiveness (VE) of 47% (95% CI: 6-70%). Notably, vaccine mismatch or a non-epidemic season was not associated with protection. Significant reductions in influenza-related hospitalizations and mortality have been observed in vaccinated elderly populations (2,4,5). Talbot et al. conducted a prospective observational study over three influenza seasons (2006-2009) to assess the effectiveness of influenza vaccination in preventing hospitalizations in community-dwelling older adults (4). The study included 39 cases and 378 controls. The researchers observed that influenza vaccination was associated with an effectiveness of 61.2% (95% CI: 17.5-81.8%) against laboratory-confirmed influenza hospitalization in adults aged 50 years and older.

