9. RESEARCH METHODS

9.1 Study design

We will take advantage of the unique nationwide register-data available to us, and construct country-specific cohorts with individual-level information on dates of vaccination and dates of effectiveness endpoints together with relevant covariate information. All Nordic residents are assigned a unique personal identifier at birth or immigration, enabling linkage between register data. Nordic countries have universal and tax-financed healthcare systems and reporting to national registers is mandatory, providing near-complete follow-up of all residents over time.

The study period will start on 1st October 2024 in the three countries. This study start date corresponds to the start of the seasonal influenza vaccination program in the three countries. The study period will end on the last date of data availability at time of analyses during spring 2025.

The study design will build on our previous work with Covid-19 vaccination effectiveness in the Nordic countries (19,20). We will utilize a cohort design in a target trial emulation (TTE) framework to estimate both relative and absolute effects. The evaluations in 65+-yr-olds and risk groups 18-64-yr-olds will be designed as two separate target trial emulations. Key components of the specification and emulation of the pragmatic target trials of the effectiveness of brand-specific seasonal IVE using Nordic nationwide register data are included below in Table 1.

Table 1. Target trial emulation framework

Protocol	Target Trial Specification	Target Trial Emulation
Eligibility criteria	
 • Individuals 65+-years-of-age (trial 1) • Individuals in risk groups 18-64-yr-of-age (trial 2) • Have a permanent residency in Denmark, Finland, or Sweden at start of study period 	Same as for the target trials.
Treatment strategies	Vaccination with any of the following influenza vaccines InfluvacTetra, VaxigripTetra, FludTetra, FluarixTetra or Efluelda Tetra, October 1, 2024 to January 31, 2025 vs vaccination with placebo in the same period.	Same as for the target trials except vaccination with placebo is replaced by no vaccination with any of the vaccines under study.

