Treatment assignment	Randomization: Eligible individuals are randomly assigned to receive influenza vaccination with a randomly chosen vaccine brand or no vaccination 1:1	Matching: Eligible individuals who are vaccinated in each country during the study period will be matched 1:1 with individuals who have not yet received a vaccine by age (5-yr bins), sex, region of residence, and presence of comorbidities. Unvaccinated individuals are assigned the index date (date of vaccination) of the matched vaccine recipient.
Outcomes	
Primary:
 
 • Hosp. due to Influenza – Lab. conf + J09-J11 • Lab. conf. Influenza A and B (combined and separately) • Death with influenza – Lab. conf within 30 days before date of death 
Secondary:
 
 • Hosp. due to ILI – J09-J11 • Hosp. due to ARI or SARI – J09-J22 • Hosp. due to Influenza with ICU admission • All-cause mortality 	Same as for the target trials.
Follow-up	Day 14 after date of vaccination or placebo will serve as the start of follow-up until the day of an outcome event, death, emigration or end of influenza season. Controls are censored if vaccinated.	Day 14 (time zero) after date of vaccination in each matched pair (index date) will serve as the start of follow-up until the day of an outcome event, death, emigration or end of influenza season (or latest possible date of data availability). Pairs are

		censored if controls are vaccinated.
Causal contrast of interest	
 • Intention to Treat – average effect of treatment assignment in trial population • Per-Protocol Effect – average effect among those who complied with their assigned treatment. 	
 • Modified Per- Protocol Effect – average effect among vaccinated (“do those who get the seasonal influenza vaccination benefit?”)
Statistical analysis	VE estimated as 1 - Risk Ratio at week 18 since index date using cumulative incidences from the Aalen-Johansen estimator.	Same as for the target trial. Week 18 subject to change according to data availability. Change will be made before any effectiveness results are estimated.

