Influenza-related death	Denmark	The Civil Registration System and the Danish Microbiology Database. Defined as (the date of) death within 30 days after PCR positive test for influenza.
	Finland	The Finnish Population Information System and the National Infectious Diseases Register. Defined as (the date of) death within 30 days after PCR positive test for influenza.
	Sweden	The Total Population Register, the Cause of Death Register, and the Swedish Patient Register and the Register on surveillance of notifiable communicable diseases (SmiNet). Defined as (the date of) death within 30 days after PCR positive test for influenza.

Furthermore, medically attended outcomes presented in Table 5 will be assessed.

Table 5. Medically attended influenza outcomes

Variable	Country	Data source and details
Influenza-like-illness	Denmark	The National Patient Register. Defined as ICD-10 diagnostic codes J09, J10 and J11 used as a primary or secondary diagnosis.
	Finland	National Care Register for Health Care. Defined as ICD-10 diagnostic codes J09, J10 and J11 used as a primary diagnosis.
	Sweden	The Swedish Patient Register. Defined as ICD-10 diagnostic codes J09, J10 and J11 used as a primary diagnosis.
Hospitalisation for acute respiratory infections (ARI) and severe acute respiratory infections (SARI)	Denmark	The National Patient Register. A hospitalised patient is a SARI patient who a) has been admitted to hospital during the study period and has not been discharged to their home or home equivalent, b) inpatient contact or at least 12 hours of contact, and c) a ARI/SARI relevant primary diagnosis code (ICD-10: J09-J22).
	Finland	National Care Register for Health Care and the National Infectious Diseases Register. A hospitalised patient is a SARI patient who a) has been admitted to hospital during the study period and has not been discharged to their home or home equivalent, b) inpatient contact or at least 12 hours of contact, and c) a ARI/SARI relevant primary diagnosis code (ICD-10: J09-J22)
	Sweden	The Swedish Patient Register and the Register on surveillance of notifiable communicable diseases (SmiNet). A hospitalised patient is a SARI patient who a) has been admitted to hospital during the study period and has not been discharged to their home or home equivalent, b) inpatient contact or at least 12 hours of contact, and c) a ARI/SARI relevant primary diagnosis code (ICD-10: J09-J22)

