Logistic regression models will be used to estimate the odds ratio (OR) with 95% CIs. Our main estimate of interest is the vaccine effectiveness defined by $(1-OR) \times 100\%$. The models will be adjusted for age, sex, region of residency and comorbidities. We will assess whether the frequency of testing differs between vaccinated and unvaccinated groups during the season, since differential testing could bias VE estimates. The testing frequency will be visualized in a plot stratified by month and vaccination status.

Prior event rate adjustment

A difference-in-differences approach in the form of prior event rate ratio (PERR) adjustment exists for evaluating healthy vaccinee bias for influenza outcomes. (51) The PERR method is built on the assumption that any differences in event rates unrelated to vaccination between vaccinated and unvaccinated individuals can be observed in the period before vaccination is available. This can be implemented using the pairwise version of PERR. (51)

The matching and censoring criteria from the main TTE analysis will be applied. As before, the day the seasonal vaccine dose was administered within each matched pair will serve as the index date for both individuals. For each individual within a matched pair, the pre-vaccination period will be the start of the 2024/2025 influenza season (1 October 2024) until the index date and the post-vaccination period will start on day 14 following the index date. We will identify individuals who ultimately receive a seasonal influenza vaccine (“future vaccinated”) and those who remain unvaccinated (“future unvaccinated”), evaluated at the end of the studied period or on the date of the outcome. Both groups will have the number of outcomes and the amount of person-time measured in the pre-vaccination period (to establish baseline event rates) and in the post-vaccination season (to assess post-vaccination event rates).

The outcome under study is influenza-related hospitalization. Given that influenza hospitalization may be less frequent at the start of the influenza season, we will assess whether sufficient events occur in the pre-vaccination period to produce stable estimates.

We will employ the pairwise version of PERR, which effectively compares the ratio of (current vs. pre-vaccinated) event rates in the vaccinated group to the ratio of (current vs. pre-vaccinated) event rates in the unvaccinated group. Formally:

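### ARI/SARI hospitalisation, a non-specific secondary outcome, is counted from day 14 whether or not influenza is circulating, and no planned analysis separates out or uses the weeks before circulation

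*Protocol*

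**What the plan says.** **Follow-up.** Protocol section 9.7 states a single rule for all outcomes: "We will follow individuals from day 14 after the index date (to ensure full immunisation) up until the day of an outcome event". VE is one minus the risk ratio "at the start of week 18 (depending on data availability) since index date". Table 1 (section 9.1) ends follow-up at the end of the influenza season or of the data, but nothing ties the start to circulation.

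**Index dates.** Table 1 sets the vaccination window as "October 1, 2024 to January 31, 2025 vs vaccination with placebo in the same period". Section 9.3 gives programme starts of 30 September (Finland), 1 October (Denmark) and 15 October (Sweden), and says that vaccination usually comes before the peak. Section 9.5 shows that uptake is early: "From 1 October 2024 to 20 December 2024, influenza vaccination coverage in these target groups was 75.6% and 29.2%, respectively" (the Danish groups aged 65+ and at risk below 65).

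**Outcome.** Table 1 lists "Hosp. due to ARI or SARI" as secondary. Table 5 asks for a hospital contact with "a ARI/SARI relevant primary diagnosis code (ICD-10: J09-J22". No positive influenza test is required, unlike the primary hospitalisation outcome in Table 4.

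**Checks in section 9.8.**
- The negative control outcomes are low back pain, clavicle fracture and diverticulitis.
- Prior event rate adjustment, regression discontinuity and the day-0 analysis use influenza hospitalisation.
- The test-negative study covers influenza infection in Denmark only.

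None of these looks at ARI/SARI before influenza circulates.

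**The concern.** A start at day 14 does little harm to laboratory-confirmed outcomes, because few or no such events occur without circulating virus. ARI/SARI is different: J09-J22 admissions from other causes happen throughout the autumn. In weeks without influenza, a pair adds events on which the vaccine has no effect, so the risk ratio moves towards one, while differences in frailty and care-seeking (Table 8) act as before.

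Two things are at stake. The first is how to read a small VE against ARI/SARI, which mixes dilution and bias in unknown proportion. The second is a missed check. The weeks before onset, in the same cohort and with the same codes, have an expected risk ratio of one if confounding is controlled. Section 9.8 says that a negative control works only if it shares the confounders of the outcome of interest. Pre-circulation ARI/SARI meets that condition more closely than the three non-respiratory outcomes, yet the plan averages it into the VE.

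**Working it through.** The protocol states no power, effect size or dilution for ARI/SARI, so there is no figure of its own to reproduce.

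**From the protocol:** start at day 14; horizon at the start of week 18, taken as day 119 (105 days at risk); index dates from 1 October; example data cut 1 March 2025 (section 4); 1:1 matching; VE in older adults of 28-42% against influenza A subtypes (multi-site evaluation, section 7).

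**Assumed, because the protocol gives none:** onset of circulation 1 December, 15 December or 1 January; k = ARI/SARI rate in circulation divided by the rate before it, 1 to 3; f = influenza share of ARI/SARI admissions in circulation, 20%; VE against influenza admissions 40%; b = residual confounding risk ratio, 0.90 to 0.99; index dates spread evenly.

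**Step 1, dilution for a single index date.** D = 1 + W_pre / (k × W_circ), where W_pre and W_circ are follow-up time before and during circulation. For index date 1 October, follow-up runs from 15 October to 28 January. With onset 15 December, W_pre = 61 days and W_circ = 44 days, so at k = 1, D = 105/44 = 2.39. At day 119:

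| Index date | k | Onset 1 Dec | Onset 15 Dec | Onset 1 Jan |
|---|---|---|---|---|
| 1 Oct | 1 | 1.81 | 2.39 | 3.89 |
| 1 Oct | 2 | 1.41 | 1.69 | 2.44 |
| 15 Oct | 1 | 1.46 | 1.81 | 2.56 |
| 15 Oct | 2 | 1.23 | 1.41 | 1.78 |
| 1 Nov | 1 | 1.18 | 1.40 | 1.81 |
| 1 Nov | 2 | 1.09 | 1.20 | 1.41 |
| 15 Nov | 1 | 1.02 | 1.18 | 1.46 |

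At k = 1, D exceeds 2 when W_pre is above 52.5 days. That means index dates up to 9 October with onset 15 December, or up to 26 October with onset 1 January. At k = 2 it needs a January onset and an index date up to 8 October. No November date reaches 2. If week 18 is read as day 126, the 1 October values at k = 1 fall to 1.72, 2.20 and 3.29.

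**Step 2, average over index dates 1 October to 30 November** (data cut 1 March):

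| Onset | Mean weeks before / in circulation | D, k = 3 to k = 1 |
|---|---|---|
| 1 Dec | 2.6 / 11.4 | 1.08 to 1.23 |
| 15 Dec | 4.4 / 9.6 | 1.15 to 1.46 |
| 1 Jan | 6.9 / 7.2 | 1.32 to 1.95 |

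Spreading index dates to 20 December instead gives 1.06 to 1.73.

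**Step 3, true VE against ARI/SARI.** In circulation: 0.40 × 0.20 = 8%. Over the whole window: 8%/1.08 = 7.4% down to 8%/1.95 = 4.1%. The step from 40% to 8% is a factor 1/f = 5; timing adds 1.1 to 2.0.

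**Step 4, confounding.** Observed VE = 1 − (1 − VE) × b.

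| True VE | b = 0.99 | b = 0.95 | b = 0.90 |
|---|---|---|---|
| 8% (circulation) | 8.9% | 12.6% | 17.2% |
| 7.4% (whole window, low dilution) | 8.3% | 12.0% | 16.7% |
| 4.1% (whole window, high dilution) | 5.1% | 8.9% | 13.7% |

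At true VE 4.1%, b = 0.95 adds 4.8 points, more than the effect. At 7.4% it adds 4.6 points, less than the effect, while b = 0.90 adds 9.3 points, more than the effect. At b = 0.99 about one point is added.

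**Step 5, what the pre-onset weeks could show.** There the expected risk ratio is b itself. By Schoenfeld's formula (two-sided 5%, 80% power, 1:1), events = 4 × (1.96 + 0.84)² / (ln b)²: about 2,829 events for b = 0.90 and 11,933 for b = 0.95. Without an ARI/SARI rate in the protocol, one cannot say how many will accrue.

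**The case against.** **Every input to the size is assumed.** This stands. The protocol supports the direction only. Its remark "Given that influenza hospitalization may be less frequent at the start of the influenza season" is a caution about event counts in the prior-event-rate analysis, not a date of onset. Section 9.5 already counts 414 Danish influenza hospitalisations at 65+ by 13 January 2025.

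**The estimand is coherent.** Risk of respiratory admission from day 14 to week 18 is a legitimate total-burden question, and a small VE is then a fair answer. This stands, and is why the planned estimate should stay.

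**The start date is not the main cause.** This stands. Non-specificity attenuates more than timing does, and a shorter window leaves b unchanged. Restriction only raises the effect relative to the bias, by D.

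**The protocol already acknowledges the issue.** Section 7 warns about non-specific outcomes, section 9.9 notes timing relative to circulation, and cumulative incidence curves will be reported per outcome. But no analysis follows from these statements for ARI/SARI.

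**This could be left to an analysis plan.** Partly so. Yet section 9.8 does set out the bias checks, and a check on this outcome's own pre-circulation period is not among them.

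A reader might also take "vaccine mismatch or a non-epidemic season was not associated with protection" (section 7) as evidence that the early weeks carry no protection. It concerns mismatch and whole non-epidemic seasons in a pooled test-negative analysis, and says nothing about weeks within a season.

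**Conclusion.** The point holds as an inexpensive improvement for one secondary outcome. Counting ARI/SARI from day 14 regardless of circulation dilutes VE by about 1.1 to 2.0 on average over October-November index dates, given the assumed onsets and rate ratios. With VE 40% and influenza share 20%, true VE goes from 8% in circulation to about 4-7% over the window. A bias risk ratio of 0.90-0.95 can then equal or exceed the effect.

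Three stronger readings are tempting and not supported:

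- **Two- to threefold dilution throughout.** Dilution above twofold appears only for October index dates combined with a mid-December or later onset, and not for all of those.
- **Any confounding swamps the effect.** A bias of 0.99 adds about one percentage point and leaves the effect visible.
- **The primary results are affected.** The laboratory-confirmed outcomes have few or no events before circulation and are largely untouched.

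**What to change.** Keep the day-14 to week-18 estimate for ARI/SARI, and add two analyses of this outcome to section 9.8.

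- **(a) Circulation period.** A risk ratio starting at the later of day 14 and a country-specific onset date. Set that date from national surveillance, without regard to vaccination status and before any effectiveness results are estimated (the condition Table 1 already places on changing week 18). Include pairs still at risk at that date, and state the horizon.
- **(b) Pre-circulation period.** The risk ratio with 95% CI from day 14 to the day before onset, reported as a negative-control period for ARI/SARI.

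The cost is a paragraph of text, one onset date per country and a second start date in the common R script. The downside: pairs censored or with an event before onset do not contribute to (a), so (a) answers a conditional question and belongs beside the planned estimate. (b) may be imprecise for late index dates, so an interval that includes one should not be read as proof of no bias. Neither analysis removes confounding; (b) shows its size for this outcome.
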